4.3.3.2 EuroQoL EQ-5D-3L

Subjects' reports of general health status will be assessed using the EuroQoL Group's EQ-5D-3L. EQ-5D-3L essentially has 2 components: the descriptive system and the visual analogue scale (VAS).

The instrument's descriptive system consists of 5 dimensions: mobility, self-care, usual activities, pain/discomfort, and anxiety/depression. Each dimension has 3 levels, reflecting "no health problems," "moderate health problems," and "extreme health problems." A dimension for which there are no problems is said to be at level 1, while a dimension for which there are extreme problems is said to be at level 3. Thus, the vectors 11111 and 33333 represent the best health state and the worst health state, respectively, described by the EQ-5D-3L. Altogether, the instrument describes $3^5 = 243$ health states. Empirically derived weights can be applied to an individual's responses to the EQ-5D-3L descriptive system to generate an index measuring the value to society of his or her current health. Such preference-weighting systems have been developed for the UK, US, Spain, Germany, and numerous other populations. For this study, EQ-5D-3L utility index values will be computed using a scoring algorithm based on the United Kingdom Time-Trade-Off (UK TTO) value set²

In addition, the EQ-5D-3L includes a VAS, which allows respondents to rate their own current health on a 101-point scale ranging from 0="worst imaginable" health to 100="best imaginable" health state³.

A change from baseline of 0.08 for the EQ-5D-3L utility index score and of 7 for the EQ-5D-3L VAS are considered minimally important differences for the EQ-5D-3L⁴.

All questionnaires completed at baseline and on-study will be assigned to a time-point according to the windowing criteria in Table 3 and included in the analysis. In case a subject has two on-study assessments within the same window, the assessment closest to the time-point will be used.

And, in the case of two assessments at a similar distance to the time-point, the latest one will be chosen. In the event where the subject has no assessment at all in a specific window, the observation will be treated as missing for that time-point.

5 SAMPLE SIZE AND POWER

Currently, there is only little reliable data describing the percentage of subjects with melanoma progressing after prior therapy containing treatment with an anti-CTLA-4 monoclonal antibody, presenting with Performance Status 2, and eligible for nivolumab treatment. It is estimated that a minimum of 20% of the potential study population will initially present with PS2. Given that approximately 20% of the 920 subjects screened is 185 subjects, it is expected that the full complement of 160 subjects will be enrolled and treated in the PS2 cohort.

With an approximate 15% screening failure rate, a cohort of 735 screened PS1 subjects is projected to yield 640 treated subjects. With $n = 640$ subjects, about 3 will experience a rare adverse event with 0.5% true cumulative event rate with a rate estimated within 95% confidence interval (CI) (0.1%-1.4%). Approximately 2 subjects with events and a 95% CI of (0%-1.1%) for assumed true event rate of 0.3% are projected.

6 STUDY PERIODS, TREATMENT REGIMENS AND POPULATIONS FOR ANALYSES

6.1 Study Period

See Section 6.1 of the Core Safety SAP.

6.2 Treatment Regimens

Subjects will be treated with 3 mg/kg of nivolumab as a 60-minute (+/-5 minutes) IV infusion on Day 1 of a treatment cycle every 2 weeks (14 days) for a maximum of 24 months. No premedications are recommended for initiation of dosing. Dosing calculations should be based on the body weight assessed at each visit. It is not necessary to re-calculate subsequent doses if the subject's weight is within 10% of the weight used to calculate the previous dose. All doses should be rounded to the nearest milligram per institutional standard. The screening body weight may be used for dosing of Cycle 1. There will be no nivolumab escalations or reductions permitted. Subjects may be dosed no less than 12 days from the previous dose.

6.3 Populations for Analyses

The following analysis populations are defined for this study:

- **All Enrolled analysis set:** All subjects who signed an informed consent form and were registered into the IVRS.
- **All Treated analysis set:** All enrolled subjects who received at least 1 dose of nivolumab
- **Response evaluable analysis set:** All enrolled subjects who received at least 1 dose of nivolumab and have both baseline and at least 1 post-baseline tumor scans.

6.4 Subpopulations for Analyses

The study will include several analyses performed according to subpopulations (cohorts). These subpopulations are summarized below. Except where otherwise stated, all analyses will be performed for all treated subjects, as overall and for each subpopulation defined in this section.

- Mucosal population: Subjects have their baseline type of melanoma as mucosal.
- Cutaneous population: Subjects have their baseline type of melanoma as cutaneous.
- Ocular/Uveal population: Subjects have their baseline type of melanoma as ocular/uveal.
- Acral: Subjects have their baseline type of melanoma as acral.
- Other subtype of melanoma: Subjects have their baseline type of melanoma as other.
- ECOG PS 2 population: Subjects have their baseline ECOG PS grade of 2.
- CNS metastasis population: Subjects will be classified into this group based on the evidence of brain metastasis at baseline. Subjects with CNS metastasis are those who answered “MIC WITH BRAIN METASTASES” on the “M Status” question of the “Initial/Current Disease Diagnosis” form of the CRF (Yes).
- BRAF Mutation population: Subjects have their baseline BRAF mutation status with Mutant defined as all mutations of V600 (e.g., V600, V600E, V600K, V600D, or V600R) and all remaining (no mutation or non-V600 mutations) defined as Wildtype.
- Autoimmune disease population: Subjects will be classified into this group if they report a history of autoimmune disease at baseline.
- Experience of immune-related AE during treatment with an anti-CTLA-4 antibody: Subjects will be classified into this group based on subject’s experience of Grade 3-4 immune-related AE during treatment with an anti-CTLA-4 antibody (Yes).

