8.4.2 Safety Analyses

8.4.2.1 Primary Analyses

The evidence for the research hypothesis of this clinical trial that high-grade (CTCAE v4.0 Grade 3 or higher), treatment-related select adverse events occur with a low frequency in patients with advanced (unresectable or metastatic) melanoma will be presented in terms of the number, percentage of patients, and 95% confidence intervals for the percentage with these select adverse events during and off-treatment overall and by cohort.

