7 STATISTICAL ANALYSES

7.1 General Methods

In the analysis described below (except where noted), counts and percentages will be reported for discrete variables with inclusion of unknown or missing values as a separate category. The mean, standard deviation, median, range (minimum and maximum), and number of non-missing values will be reported for each continuous measure.

Adverse events and medical history will be coded according to the most recent Medical Dictionary for Regulatory Activities (MedDRA). Previous and [REDACTED] will be coded using the WHO Drug Dictionary.

The time to event distribution (i.e. overall survival) will be estimated using Kaplan Meier techniques. Median for time to event endpoints along with 95% confidence interval (CI) will be constructed based on 95% CI using the Brookmeyer and Crowley¹ method. Overall survival rates at selected time points, including survival rates at Years 1 and 2, together with their 95% CIs will also be estimated using KM estimates on the OS curves. Associated 2-sided 95% CIs will be calculated using the Greenwood formula.

All data summaries, unless otherwise noted, will be presented by subpopulations. A total column will be included in each summary.

- Mucosal
- Cutaneous
- Ocular/Uveal
- Acral
- Other
- ECOG PS2
- CNS Metastasis
- Autoimmune disease
- Grade 3-4 irAEs with anti-CTLA-4

Tables that will be presented by baseline LDH, BRAF mutation and type of autoimmune disorder should have the following presentation order:

- Baseline LDH: \leq ULN, $>$ ULN, and $> 2*ULN$
- BRAF status: Mutant, Wildtype, and Not reported, if no BRAF genetic mutation results are available.
- Type of autoimmune disorder: Endocrine, Gastrointestinal, Hepatic, Skin, and Other

Further, general methods information for the safety analysis, including general methods for adverse events and laboratory tests can be found in Section 7.1 of the CA209 Core Safety SAP version 4. Statistical analyses will be carried out using SAS software (SAS Institute, Cary, North Carolina, USA), unless otherwise noted.

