7.2 Study Conduct

7.2.1 *Accrual*

The accrual pattern will be summarized per country, investigational site, and per month for all treated subjects. Informed consent date, first dosing date, country, and investigational site will be presented in a by subject listing of accrual.

7.2.2 *Relevant Protocol Deviations*

Relevant deviations from the study protocol will be summarized and listed by subjects on the population of all treated subjects.

At entrance:

- Subjects with baseline ECOG Performance Status > 2 .
- Subjects with no prior systemic anti-cancer therapy.
- Subjects with no histologically documented stage III or IV melanoma.
- Subjects without measurable disease at baseline.
- Subjects who have not received anti-CTLA-4 therapy or have not progressed on or after anti-CTLA-4 therapy.

On study:

- Subjects receiving concurrent anti-cancer therapy.

Each subject's data will be examined for deviation from protocol criteria (including violation of eligibility criteria, discrepancies between enrolled and treatment received and on-study deviations).

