7.3.2 Demography and Subject Characteristics

The demographic characteristics, physical measurements, and other baseline characteristics of subjects will be reported using the all treated analysis set, overall and by subpopulations.

The following demographic characteristics, physical measurements, and other baseline characteristics will be summarized. The age of a subject will be defined as the truncated difference in years between the date of the informed consent and the date of birth, plus 1 day (e.g. $((DD/MM/YYYY2 - DD/MM/YYYY1) + 1/365.25) = \text{result in years to 1 decimal place (xx.x)}$).

Frequency and percentage will be reported, unless otherwise noted.

Demographics characteristics:

- Age (< 65; ≥ 65 and < 75; ≥ 75 and < 85; ≥ 65; ≥ 75; ≥ 85; summary statistics) (years)
- Sex (Male, Female)
- Race (White, Black or African American, American Indian or Alaska Native, Asian, Native Hawaiian or Other Pacific Islander, Other, Not Reported)
- Ethnicity (Hispanic/Latino, Not Hispanic/Latino, Not Reported)

Physical measurements summary:

- Baseline weight (summary statistics) (kg)
- Baseline height (summary statistics) (cm)
- Baseline BMI (summary statistics) (kg/m²)
- ECOG Performance Status (0-1, 2, Not Reported)

Other baseline characteristics:

- Subtype of Melanoma (Mucosal, Cutaneous, Acral, Ocular/Uveal, Other)
- BRAF Mutation status (Wild type, Mutant, Not Reported)

- Current disease stage (Stage III, Stage IV, Unknown)
- M-stage at study entry (M0, M1A, M1B, M1C, Unknown)
- Brain metastasis (Yes, No)
- Treatment status of CNS metastasis (Treated, Untreated, Leptomeningeal)
- Number of prior therapies (1, 2, >=3)
- Baseline LDH (<=ULN, >ULN, <=2*ULN, >2*ULN)
- Type of autoimmune disorder (Endocrine, Gastrointestinal, Hepatic, Skin, and Other)
- Condition of autoimmune disorder (Active, Not Active)

A subject listing of demography and subject characteristics will be produced on the all treated analysis set.

A summary of demographic characteristics, physical measurements, and other baseline characteristics will also be presented by baseline LDH, BRAF status, and type of autoimmune disorder.

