7.5 Efficacy

7.5.1 Overall Survival and Overall Response Rate at Week 12

Overall survival is defined as the time between the start of treatment and the date of death due to any cause. A subject who has not died will be censored at last known date alive.

Overall survival will be summarized using Kaplan-Meier (KM) product-limit method and associated statistics in the all treated analysis set by subpopulations. Median values of OS, if estimable, along with 2-sided 95% CI using the Brookmeyer and Crowley method will be calculated. If medians are not estimable, other percentiles (e.g., 10th and 25th) may be reported. OS

rates at selected time points, including survival rates at 6 months, 12 months, 18 months, and 24 months, together with their 95% CIs will also be estimated using KM estimates on the OS curves. Minimum follow-up must be longer than the timepoint of interest to generate the OS rate for that particular timepoint. For example, if the timepoint of interest is 6 months and the interval of enrollment date and last patient last visit is less than 6 months, then, the minimum follow-up is not reached and OS rate is not generated. Associated 2-sided 95% CIs will be calculated using the Greenwood formula.

A swimming plot showing the response, progression, duration of therapy and death will be presented using the all treated analysis set, overall and by ECOG PS 2, Ocular/Uveal, and Mucosal subpopulations only.

The overall response rate is defined as the number of subjects with a complete response (CR) or partial response (PR) at week 12 divided by the number of subjects treated. The overall response will be summarized by binomial response rates and their corresponding two-sided 95% exact CIs using the Clopper-Pearson method. A by subject listing will be provided.

A summary of overall response will also be presented by baseline LDH, BRAF status, and type of autoimmune disorder.

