7.5.3 Subgroups Analyses

OS among treated population will also be summarized within subsets at baseline (with two-sided 95% CI for the medians calculated via log-log transformation.).

- Age (< 65, ≥ 65)
- Gender (male, female)
- M-Stage at diagnosis
- Number of lines of prior systemic treatment in metastatic setting (add footnote for only metastatic setting)
- Baseline LDH (≤ ULN, >ULN, >2xULN)

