7.6.1 Primary Analysis

7.6.1.1 High-grade (CTCAE v4.0 Grade 3 or higher) Treatment-Related, Select Adverse Events.

The number and percentage of subjects who report high-grade (CTCAE v4.0 Grade 3 or higher), treatment-related, select adverse events pulmonary, gastrointestinal, skin, renal, hepatic, pancreatic, neurologic, endocrine) will be summarized using the all treated analysis set by system organ class and Medical Dictionary for Regulatory (MedDRA) preferred term. In addition, the number, percentage of subjects, 95% CI for the percentage of subjects with these select AEs will also be presented by subpopulations.

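### The SAP specifies no outcome estimates for Cohort 1 (ECOG PS 0-1), although the protocol promises results by cohort; separately, the synopsis misstates the confidence interval for a 0.5% event rate at n = 640

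*SAP*

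**What the plan says.** **Protocol.** Section 8 defines two cohorts by performance status: Cohort 1 (PS 0-1, 640 treated) and Cohort 2 (PS 2, at most 160 treated). Section 8.4.2.1 promises the number, percentage and 95% confidence interval for the "percentage with these select adverse events during and off-treatment overall and by cohort". Section 8.4 promises the primary and secondary endpoints by ECOG PS cohort, and response rate by PS. The Analyses part of the synopsis promises OS summaries by cohort.

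**SAP.** Table 1 repeats the two-cohort design. The analysis groups are set in 6.4, where the only group based on performance status is "ECOG PS 2 population: Subjects have their baseline ECOG PS grade of 2". Section 7.1 states that "All data summaries, unless otherwise noted, will be presented by subpopulations"; its column list has ECOG PS 2 and a total, with no PS 0-1. The outcome sections rely on these lists:

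- Primary endpoint (7.6.1.1): "95% CI for the percentage of subjects with these select AEs will also be presented by subpopulations".
- OS by Kaplan-Meier (7.5.1): "associated statistics in the all treated analysis set by subpopulations".
- Further OS subsets (7.5.3): "OS among treated population will also be summarized within subsets at baseline". The subsets are age, gender, M-stage, prior lines and LDH.

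PS 0-1 is a summary category only in the baseline table of 7.3.2: "ECOG Performance Status (0-1, 2, Not Reported".

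**Precision statement.** For n = 640, a 0.5% true rate and about 3 events, the synopsis gives a 95% interval of 0.2%-1.1%. Protocol 8.1 and SAP 5 give 0.1%-1.4% for the same inputs. All three give 0%-1.1% for a 0.3% rate with about 2 events.

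**The concern.** A programmer following this SAP would produce results for PS 2 and for everyone pooled, and none for PS 0-1. The missing group is the larger cohort and the one for which the planned precision was stated. The pooled column does not replace it, because it includes up to 160 PS 2 patients, whose risk-benefit ratio the protocol has monitored separately.

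The loss is greatest for OS: a Kaplan-Meier curve, median or survival rate for PS 0-1 cannot be obtained from the pooled and PS 2 summaries.

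The synopsis interval is a smaller matter. It disagrees with the protocol body and the SAP, and it makes the planned precision look better than it is.

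**Working it through.** **1. Cohort results: promise against plan**

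| Output | Protocol promise | Where | SAP groups | PS 0-1 included? |
|---|---|---|---|---|
| Primary incidence with 95% CI | Overall and by cohort | 8.4.2.1, synopsis | 7.6.1.1, by the 6.4/7.1 lists | No |
| Secondary safety endpoints | By ECOG PS cohort | 8.4 | 7.6, by the 6.4/7.1 lists | No |
| OS | By cohort | 8.4, synopsis | 7.5.1, by the 6.4/7.1 lists; 7.5.3 subsets | No |
| Response rate | By PS | 8.4 | 7.5.1, under the general rule in 6.4 and 7.1; also by LDH, BRAF and autoimmune type | No |
| Baseline characteristics | By cohort and subgroup | 8.4.1 | 7.3.2 | As a row only |

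Share of planned treated patients in Cohort 1: 640 / 800 = 80%.

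*What subtraction can recover.* For a binary endpoint, total minus PS 2 leaves a count and a denominator. That remainder also holds any subject whose PS is not reported (a category in SAP 7.3.2) and any in the deviation category "Subjects with baseline ECOG Performance Status > 2" (SAP 7.2.2). For OS, the pooled curve depends on the combined risk sets at every event time, so its median and rates cannot be separated using the PS 2 summary.

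**2. The interval for a 0.5% rate**

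Inputs, from the synopsis, protocol 8.1 and SAP 5: n = 640 and true rates of 0.5% and 0.3%.

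Expected events: 640 × 0.005 = 3.2 (about 3) and 640 × 0.003 = 1.92 (about 2), as stated.

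The Clopper-Pearson 95% limits for x events in n are:

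- lower = 0.025 quantile of Beta(x, n − x + 1)
- upper = 0.975 quantile of Beta(x + 1, n − x)

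Reproducing the plan's figures:

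- x = 2: 0.038%-1.124%. This rounds to the stated 0%-1.1%, which suggests that the documents use the exact method.
- x = 3: 0.097%-1.364%. This rounds to 0.1%-1.4%, as in protocol 8.1 and SAP 5.
- x = 3.2 (unrounded): 0.111%-1.410%, with the same rounding.

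Other 95% methods for 3/640 (0.469%):

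| Method | 95% interval |
|---|---|
| Wilson | 0.160%-1.369% |
| Agresti-Coull | 0.092%-1.437% |
| Jeffreys | 0.132%-1.246% |
| Mid-P | 0.119%-1.270% |
| Poisson | 0.097%-1.370% |
| Logit | 0.151%-1.443% |
| Wald | 0%-0.998% |

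None rounds to 0.2%-1.1%, and no whole number of events in 640 gives that interval by Clopper-Pearson. Clopper-Pearson does give it at larger n, for example 5 events in 1012-1083 patients. An 80% interval with 3.2 events (0.192%-1.082%) also rounds to it, but the text says 95%.

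Size of the error: the exact width is 1.364 − 0.097 = 1.267 points and the synopsis width is 1.1 − 0.2 = 0.9 points, so 0.9 / 1.267 = 0.71. The upper limit is 1.364 − 1.1 = 0.264 points too low. The synopsis gives 1.1% as the upper limit at both rates, whereas the exact limits are 1.12% for 2 events and 1.36% for 3.

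**The case against.** The strongest reply is that this is a line left out of a list, not a decision to drop Cohort 1. The protocol commitment still stands, SAP Table 1 keeps the cohort, and output layouts are left to the Data Presentation Plan, with safety detail in the Core Safety SAP. Either document could carry a PS 0-1 column. In addition, the primary proportion needs only a count and a denominator, so a Cohort 1 interval could be computed from the total and PS 2 columns. Contamination by unreported PS or PS above 2 should be small, because PS 0-2 is an entry requirement.

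Part of this stands. For binary endpoints the information is largely recoverable, and the finding can speak only for this SAP, since the other two documents were not available. But the SAP does not specify the subtraction or how to handle the stray categories, and the survival results cannot be recovered that way at all. The protocol names the SAP as the place for further analysis detail, so the group belongs there.

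A second objection is that the response rate in SAP 7.5.1 (response at Week 12 among all treated) is not the protocol's (confirmed best response in response-evaluable patients), so an added column would not deliver the promised quantity. That is correct, but it is a separate discrepancy.

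A third is that the synopsis interval is editorial. That is also correct: n = 640 and every analysis are unaffected.

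**Conclusion.** Both points hold. The SAP as written specifies no incidence interval, Kaplan-Meier median, survival rates or response rate for Cohort 1, against explicit protocol commitments and for 80% of the planned treated patients. The practical loss is mainly in OS. The conclusion rests on the visible SAP text, whose group lists show no redaction among their items; the Data Presentation Plan or Core Safety SAP might supply the column.

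The synopsis interval of 0.2%-1.1% is wrong for about 3 events in 640 by every 95% method tried. It should read 0.1%-1.4%, as the protocol body and the SAP already do. Its effect is confined to overstating the planned precision.

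The change should be made, chiefly because of the missing Cohort 1 estimates.

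**What to change.** 1. In SAP 6.4, add an ECOG PS 0-1 population (Cohort 1): subjects with a baseline ECOG PS of 0 or 1, parallel to the existing PS 2 definition. Add it to the column list in 7.1, so that the primary incidence with its 95% interval, the secondary adverse-event summaries, OS and response rate are given for PS 0-1, PS 2 and total.
2. State which PS value governs if screening and baseline differ: SAP 2.2 places subjects in cohorts at screening, while SAP 8.1 defines baseline as the last value before the first dose.
3. In the protocol synopsis, replace 0.2%-1.1% with 0.1%-1.4%.

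The cost is one more column in the tables, a clarifying sentence and one corrected figure. No patients, data or methods are added. The synopsis will state a slightly less favourable precision.

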7 STATISTICAL ANALYSES

7.1 General Methods

In the analysis described below (except where noted), counts and percentages will be reported for discrete variables with inclusion of unknown or missing values as a separate category. The mean, standard deviation, median, range (minimum and maximum), and number of non-missing values will be reported for each continuous measure.

Adverse events and medical history will be coded according to the most recent Medical Dictionary for Regulatory Activities (MedDRA). Previous and [REDACTED] will be coded using the WHO Drug Dictionary.

The time to event distribution (i.e. overall survival) will be estimated using Kaplan Meier techniques. Median for time to event endpoints along with 95% confidence interval (CI) will be constructed based on 95% CI using the Brookmeyer and Crowley¹ method. Overall survival rates at selected time points, including survival rates at Years 1 and 2, together with their 95% CIs will also be estimated using KM estimates on the OS curves. Associated 2-sided 95% CIs will be calculated using the Greenwood formula.

All data summaries, unless otherwise noted, will be presented by subpopulations. A total column will be included in each summary.

- Mucosal
- Cutaneous
- Ocular/Uveal
- Acral
- Other
- ECOG PS2
- CNS Metastasis
- Autoimmune disease
- Grade 3-4 irAEs with anti-CTLA-4

Tables that will be presented by baseline LDH, BRAF mutation and type of autoimmune disorder should have the following presentation order:

- Baseline LDH: \leq ULN, $>$ ULN, and $> 2*ULN$
- BRAF status: Mutant, Wildtype, and Not reported, if no BRAF genetic mutation results are available.
- Type of autoimmune disorder: Endocrine, Gastrointestinal, Hepatic, Skin, and Other

Further, general methods information for the safety analysis, including general methods for adverse events and laboratory tests can be found in Section 7.1 of the CA209 Core Safety SAP version 4. Statistical analyses will be carried out using SAS software (SAS Institute, Cary, North Carolina, USA), unless otherwise noted.

